## **9.4 Biometrical Evaluation**

### **9.4.1 Main Analysis**

As soon as the last subject has completed FU 2 and after any necessary settlement of queries etc. in the eCRFs a data review meeting will be held and the subjects will be assigned to the datasets as described in [Section 9.3](#). After the data review meeting and necessary settlement of queries that may arise during the data review meeting, the database will be locked. The final analysis will then be performed and will include all immunogenicity and safety data up to and including FU 2. Results of the final analysis will be reported in the Clinical Study Report (CSR).

### **9.4.2 Presentation of Data**

For biometrical analysis, data obtained in this trial and documented in the eCRFs will be listed. For parameters of interest, summary tables with descriptive group statistics for metrical variables will be prepared. For categorical / dichotomous variables summary tables showing the absolute and relative count in each category will be prepared.

Full details of the analyses will be defined in the Statistical Analysis Plan (SAP). The SAP will be finalized prior to the respective database lock. The CRO will be responsible for data management and statistical evaluation. Data will be analyzed using SAS®.

Antibody titers and derived parameters, e.g. GMTs and seroconversion rates, will be assessed by vaccinia-specific ELISA and vaccinia-specific PRNT methods as described in [Section 7.1](#).

Clinical laboratory test results will be marked whether the result is below, within or above the respective reference range. The number of values outside of the corresponding reference range will be counted.

All ECGs will be evaluated by a centralized procedure as described in the ECG Assessment Plan. Detailed descriptive analysis of the reasons/category of ECG abnormalities will be performed.

The occurrence of solicited local and general AEs during the 8-day period post vaccination (Days 0–7) will be summarized on a per subject and per vaccination basis.

Unsolicited AEs will be coded using MedDRA coding terminology. The intensity of AEs will be graded according to [Section 8.2](#).

AESIs will be separately listed and tabulated.

SAEs will be listed separately. Each SAE will be described individually in detail.

## **10 Ethical Aspects**

### **10.1 Ethical and Legal Regulations**

The PIs are to ensure that this clinical trial is conducted in complete accordance with the provisions of the 2013 version of the Declaration of Helsinki, the national laws and other guidelines for the conduct of clinical trials like the ICH GCP to guarantee the greatest possible subject protection.

### **10.2 Approval by an IEC / IRB**

The clinical trial protocol must be reviewed by the competent IEC / IRB according to the national laws of the respective CTS before the first subject is included in this trial.

If one of the investigators is a member of one of these committees, he/she may not vote on any aspect of the review of this protocol.

The Sponsor will assure that the IEC / IRB is informed of any amendment to the protocol and any unanticipated problems involving risks to human subjects included in the trial. Such information will be provided to the IEC / IRB at intervals appropriate to the degree of subject risk involved, but not less than once a year. Copies of all correspondence between the investigator and the IEC / IRB must be forwarded immediately to the Sponsor. In case of withdrawal of IEC / IRB approval of the trial, the Sponsor has to be contacted immediately by facsimile, e-mail or telephone.

### **10.3 Confidentiality and Data Protection**

The PI of the respective CTS is obliged to ensure anonymity of the subject. He/she has to make sure that all documents including eCRFs provided (e.g. in the course of a marketing authorization procedure) to third parties (in this case: to the manufacturer of MVA-BN® smallpox vaccine or to an authority) contain no subject names.

Only a subject and site number may identify subjects. Their name or clinic and subject's medical record number may not be used. The PI keeps separate confidential subject logs for trial enrollment which allows subject numbers to be matched with names and addresses of subjects at any time. Documents not meant to be passed on to third parties have to be stored securely by the PI.

Any information collected in the course of the trial may be made available only to persons directly involved in this trial (PI and his staff members, monitors, statisticians) or to authorized

persons by the Sponsor or the PI or authorities. The Sponsor of the trial will only receive pseudonymized data for analysis.

## **11 Informed Consent**

No subject can participate in this trial without having given informed consent in writing after the investigator or his delegate has informed the subject clearly and completely, verbally and in writing, over the purpose, procedures, the potential future use of blood samples and potential benefits and risks of the trial prior to any trial specific procedure.

One signed copy of the Informed Consent including HIPAA must be given to each subject and one signed copy must remain in the Investigator Site File and be available for verification by the monitor, Sponsor/CRO auditor or competent regulatory authorities at any time.

Subjects must be informed unequivocally that they may refuse participation in the trial and that they may withdraw from the trial at any time and for whatever reason and that withdrawal of consent will not affect their subsequent medical treatment or relationship with the treating physician.

Subjects also consent to authorize the monitor, quality assurance personnel and regulatory authorities to inspect source documents for data verification and quality assurance purposes. Such verifications will always be conducted at the CTS and under the ethical supervision of the investigator. All aspects of the confidentiality of the subject's data will be guaranteed.

The Informed Consent will be prepared in accordance with ICH GCP guidelines and must be approved by the appropriate IEC / IRB.

## **12 eCRFs and Retention of Records**

### **12.1 eCRF**

In this trial, the use of an eCRF is planned.

All eCRFs are to be filled out completely by the trial personnel, then reviewed and signed electronically by the PI to confirm their correctness in a timely manner. It is the PI's responsibility to ensure that all subject data entered including discontinuations or changes in trial or other medications in the eCRF are accurate and supported by the subject's medical records unless the eCRF has been declared as source documentation by BN. The eCRFs for any subject leaving the trial should be completed at the time of the final visit or shortly thereafter.

### **12.2 Retention of Records**

Essential documents as listed in ICH GCP need to be archived according to ICH GCP or national law, whatever is longer.

To meet regulatory requirements, the original source data and an electronic copy of the eCRF data will be stored at the respective CTS. The eCRF data will be stored and archived according to the Clinical Data Interchange Standards Consortium (CDISC) Operational Data Modeling (ODM) (see [www.cdisc.org](http://www.cdisc.org) for details). Since CDISC ODM is also the source for the Electronic Data Capture web-based system, no transcription of data is necessary. If needed, paper copies (file printouts) can be created from the ODM file.

### **12.3 Monitoring of the Trial**

The CRO (contact information to be found in the “Responsibilities” section in the beginning of this protocol) will be contracted to perform monitoring services according to ICH GCP.

Monitoring will be conducted according to the monitoring plan which must be approved by BN and the CRO. The monitoring plan will specify in detail the items for source data verification and other tasks, to be performed by the Clinical Research Associate (CRA) during the CTS visit.

The CRA is responsible for obtaining an overview of the course of the trial in co-operation with the investigators, checking if the clinical trial protocol is being observed, and helping the investigators to solve any problems which may arise. All documents in the context with this clinical trial will be handled confidentially at all times.

The PI has agreed to give the CRA access to relevant hospital or clinical records to confirm their consistency with the eCRF entries and to obtain an adequate overview of the course of the trial. The CRA verifies that the entries in the eCRF are complete, accurate and supported by source documents. In addition the CRA will verify that all required data documented in the source were transferred accurately in the eCRF. This will be done under preservation of data protection.

The source data verification must be performed by direct insight in the subject’s record. If a subject refuses to consent to this procedure, he/she may not be enrolled in the trial. The CTS will provide direct access to all trial related data for the purpose of monitoring and inspection by local and regulatory authorities. The PI (or a representative) has further agreed to support the monitor in solving any problems he/she discovers during his/her visits.

## **13 Audits and Inspections**

Audits and inspections may be carried out by the quality assurance department (BN and/or CRO), local authorities, or authorities to whom information on this trial has been submitted. All documents pertinent to the trial must be made available for such audits / inspections. Informed consent of subjects participating in this trial has to include the consent in this access to source documents.

## **14 Responsibilities of the PI**

The PI agrees to carry out the trial in accordance with the guidelines and procedures outlined in this clinical trial protocol. The PI especially consents to strictly adhere to the ethical principles (see [Section 10](#) of this protocol).

Changes to the protocol require written “Amendments to the protocol” and written approval by the IEC/IRB, the Coordinating Investigator and the PI of the respective CTS. Changes are allowed only if the trial value is not reduced and if they are ethically justifiable. The amendment must be passed on to all participating investigators with the obligation to adhere to its provisions. If warranted, the subject information has to be changed accordingly.

It is within the responsibility of the investigator that the eCRF has to be completed in a timely manner after each subject visit and electronically signed after the subject has finished the trial for each subject participating in the trial.

At the conclusion of the trial, the investigator will return all partly used, unused and empty drug containers to the Sponsor or the drug containers will be destroyed at the CTS according to local legal requirements.

The investigator may ask to terminate participation in the trial due to administrative or other reasons. If this should be the case, appropriate measures which safeguard the interests of the participating subjects must be taken after verification and consultation with the PI.

Each investigator will maintain appropriate medical and research records for this trial, in compliance with ICH E6 (R1) Guideline for GCP, Section 4.9, and regulatory and institutional requirements for the protection of confidentiality of subjects. He/she will permit authorized representatives of the Sponsor and regulatory agencies to review (and, when required by applicable law, to copy) clinical records for the purposes of quality reviews, audits/inspections, and evaluation of the trial safety and progress.

The PI agrees to follow the detailed publication policy included in the clinical trial agreement.

By signing this protocol, the PI confirms that he/she has read the entire clinical trial protocol, agrees to its procedures, and will comply strictly with the formulated guidelines.

## 16 Appendices

### 16.1 Appendix I: Toxicity Scale for Laboratory Values

Grade 1 or Grade 2 toxicity is only graded according to [Table 6](#) and [Table 7](#), if the value is outside of the institutional normal range applicable for this trial. Any laboratory value that is between either the LLN or ULN and Grade 1 should not be graded. The values provided in [Table 6](#) and [Table 7](#) are based on the 'Division of AIDS Table for Grading the Severity of Adult and Pediatric Adverse Events' Version 1.0, December 2004, Clarification August 2009.

#### Estimating severity grade

For abnormalities NOT found elsewhere in the Toxicity Tables use the scale below to estimate grade of severity:

- Grade 1      An AE which is easily tolerated by the subject, causing minimal discomfort and not interfering with daily activities.
  
- Grade 2      An AE which is sufficiently discomforting to interfere with daily activities.
  
- Grade 3      An AE which prevents daily activities. Such an AE would, for example, prevent attendance at work and would necessitate the administration of corrective therapy.
  
- Grade 4      Life-threatening or disabling.

#### Serious or life-threatening AEs

ANY clinical event deemed by the clinician to be serious or life-threatening should be considered a Grade 4 event. Clinical events considered to be serious or life-threatening include, but are not limited to: Seizures, coma, tetany, diabetic ketoacidosis, disseminated intravascular coagulation, diffuse petechiae, paralysis, acute psychosis, severe depression.

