## 1.5 Protocol Synopsis

Title Randomized, open-label Phase II trial to assess the safety and immunogenicity of MVA-BN® smallpox vaccine when increasing the number of injections compared to the standard regimen in immunocompromised subjects with HIV infection

[figure not shown]
---

Clinical phase Phase II

---

Sponsor Bavarian Nordic A/S

(b) (1) (A)

Coordinating Investigator

(b) (1) (A)

Number of sites and Country/ies Up to 10 sites in the USA

---

Vaccination dose and schedule

Group 1:  
One injection at Day 0 and Day 28 with 0.5 ml Modified Vaccinia Ankara Strain – Bavarian Nordic (MVA-BN®) smallpox vaccine containing at least  $1 \times 10^8$  Tissue Culture Infectious Dose 50% (TCID50) per ml (standard regimen)

Group 2:  
Two injections at Day 0 and two injections at Day 28 with 0.5 ml MVA-BN® smallpox vaccine each containing at least  $1 \times 10^8$  TCID50 per ml (double dose regimen)

Group 3:  
One injection at Day 0 and Day 28 with 0.5 ml MVA-BN® smallpox vaccine containing at least  $1 \times 10^8$  TCID50 per ml (standard regimen) and one booster injection at week 12 (booster regimen)

---

---

---

Route of administration	Each MVA-BN ® vaccination is administered subcutaneously (s.c.) in the upper arm.
Trial duration	Up to 75 weeks per subject
Sample size	90 (30 subjects per group)
Primary objective	To assess the safety of MVA-BN ® smallpox vaccine when increasing the dose or number of injections compared to the standard 2-dose regimen
Secondary objectives	To compare the immunogenicity and safety of three different vaccination strategies of MVA-BN ® smallpox vaccine
Primary endpoint	Occurrence, relationship and intensity of any serious and / or unexpected Adverse Event at any time during the trial.

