##### 8.1.2.1 Unsolicited AEs

Unsolicited AEs are defined as any untoward (undesirable) occurrence of a medical event in a clinical trial subject temporally associated with the administration of an IMP or a medical product (MP) which does not necessarily have a causal relationship with this IMP/MP. For Group 1 and 2 up to Visit 5 (Week 8) and for Group 3 up to Visit 8 (Week 16) all AEs (e.g. feeling of ill-health, subjective symptoms and objective signs, intercurrent diseases, accidents, etc.) observed by the investigator and/or reported by the subject must be recorded in the eCRF regardless of the assessment of causality in relationship with the IMP/MP.

Abnormal laboratory values assessed as being clinically significant by the investigator are to be documented as AEs. In addition, abnormal laboratory values fulfilling the Grade 3 or Grade 4 criterion according to the toxicity scale ([Section 16.1](#); [Appendix I: Toxicity Scale for Laboratory Values](#)) are to be documented as AE in the eCRF, regardless of whether they are considered clinically relevant or not. For lab values fulfilling the Grade 3 or 4 criterion, the decision to repeat the labs is left at the discretion of the PI. Toxicity grade and seriousness of an AE will be assessed separately, i.e. a Grade 3 or Grade 4 AE will not automatically be regarded as serious.

The investigator should ask the subject if they have experienced any AEs since their last visit. All intercurrent diseases reported by the subject, need to be recorded by the investigator in the appropriate section of the eCRF.

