### **8.1.2.4 SAEs**

A SAE is any untoward medical occurrence that at any dose:

- Results in death
- Is life-threatening
- The term "life-threatening" in the definition of "serious" refers to an event in which the patient was at risk of death at the time of the event; it does not refer to an event which hypothetically might have caused death, if it were more severe.
- Requires in-patient hospitalization or prolongation of existing hospitalization
- Results in persistent or significant disability or incapacity
- Results in a congenital anomaly or birth defect
- or is an otherwise important medical event, e.g. leads to suspicion of transmission of an infectious agent

Medical and scientific judgment should be exercised in deciding whether expedited reporting is appropriate in other situations, such as important medical events that may not be immediately life-threatening or result in death or hospitalization but may jeopardize the subject or may require intervention to prevent one of the other outcomes listed in the definition above. These should also usually be considered serious.

Examples of such events are intensive treatment in an emergency room or at home for allergic bronchospasm; blood dyscrasias or convulsions that do not result in hospitalization; or development of drug dependency or drug abuse.

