### Assessment of Intensity

For all unsolicited AEs not represented in the toxicity scale for Laboratory Values ([Section 16.1; Appendix I: Toxicity Scale for Laboratory Values](#)), the maximum intensity will be based on the following descriptions:

- Grade 1     An AE which is easily tolerated by the subject, causing minimal discomfort and not interfering with daily activities.
- Grade 2     An AE which is sufficiently discomforting to interfere with daily activities.
- Grade 3     An AE which prevents daily activities. (Such an AE would, for example, prevent attendance at work and would necessitate the administration of corrective therapy.)

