## 8.2.8 Safety Laboratory Measurements

The intensity of laboratory / systemic quantitatively measured toxicities will be graded according to the toxicity scale in [Section 16.1; Appendix I: Toxicity Scale for Laboratory Values](#). These grading scales include the laboratory values determined with the routine safety parameters. In case of other laboratory values not included in the routine safety laboratory and not listed in [Section 16.1; Appendix I: Toxicity Scale for Laboratory Values](#), the [Division of AIDS Table for Grading the Severity of Adult and Pediatric Adverse Events, Version 1.0](#), December 2004, Clarification August 2009 will be used for grading of laboratory toxicities.

Safety laboratory is determined at SCR, Visit 2, Visit 4, Visit 7 (Group 3 only) and at any other visit(s) if clinically indicated. The safety laboratory measurements are performed at a central laboratory. Laboratory normal ranges are provided by the central laboratory and filed in the Investigator File. Safety laboratory parameters to be evaluated are:

Hematology: Red blood cell count, hemoglobin, total and differential White Blood Cell count (WBC), platelet count (Hematocrit, mean corpuscular/cell volume (MCV), mean corpuscular/cellular hemoglobin (MCH) , mean corpuscular hemoglobin concentration (MCHC) and red blood cell distribution width (RDW) are routinely performed as part of the complete blood cell count and will be included in the laboratory report).

HIV specific parameters: CD4 count will be determined with every safety laboratory and at Visit 8 and FU 1 and FU 2. Viral load will be determined at SCR and at Visit 2. Viral load will be determined at any other visit if clinically indicated.

Serum chemistry:

Total bilirubin, AP, AST, ALT, serum creatinine (for calculation of CrCl at SCR), sodium, potassium, calcium, troponin I (troponin mandatory at SCR and in addition Visit 2, Visit 4 and Visit 7 (Group 3 only)).

Pregnancy test:

A  $\beta$ -human choriongonadotropin (HCG) pregnancy test will be conducted for all WOCBP at SCR, within 24 hours prior to each vaccination and at the individual last active trial phase visit (i.e. Visits 1, 3, 5 and Visits 6 and 8 for Group 3 respectively). At SCR a serum  $\beta$ -HCG pregnancy test will be performed; all other pregnancy tests will be conducted as urine  $\beta$ -HCG tests.

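### Unsolicited clinical adverse events have two intensity scales (Grades 1–3 and Grades 1–4), and a rule in Appendix I can set Grade 4 whatever the intensity

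*Protocol*

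**What the plan says.** Protocol 8.2.5, *Assessment of Intensity*, sets a scale "For all unsolicited AEs not represented in the toxicity scale for Laboratory Values". It defines Grades 1, 2 and 3 by their effect on daily activity and stops there.

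Protocol 16.1 (Appendix I), *Estimating severity grade*, says: "For abnormalities NOT found elsewhere in the Toxicity Tables use the scale below to estimate grade of severity". Its first three grades match 8.2.5, and it adds Grade 4 for events that threaten life or disable. The next paragraph, *Serious or life-threatening AEs*, says: "ANY clinical event deemed by the clinician to be serious or life-threatening should be considered a Grade 4 event". Its open-ended examples include seizures, coma, paralysis, diffuse petechiae and severe depression. It neither defines *serious* nor refers to the SAE definition in 8.1.2.4, one criterion of which is: "Requires in-patient hospitalization or prolongation of existing hospitalization".

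Protocol 8.1.2.1 says that toxicity grade and seriousness are "assessed separately, i.e. a Grade 3 or Grade 4 AE will not automatically be regarded as serious".

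Three places bear on which scale governs:
- Protocol 9.4.2: "The intensity of AEs will be graded according to" Section 8.2, which contains both 8.2.5 and 8.2.8.
- Protocol 8.2.8: "The intensity of laboratory / systemic quantitatively measured toxicities will be graded according to the toxicity scale in" Appendix I.
- SAP 3.5.9 refers the reader to the protocol for grading and names no section.

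The primary endpoint (Protocol 1.5) is: "Occurrence, relationship and intensity of any serious and / or unexpected Adverse Event at any time during the trial".

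**The concern.** Both residual scales claim the same events, namely clinical events that the laboratory tables do not cover. They end at different grades, and Appendix I then adds a rule that can override either one. Investigators at up to 10 open-label sites could grade the same event differently and each be following the protocol.

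Intensity of serious events is part of the primary endpoint. The planned SAE table (15.3.2.1) gives incidence by term without intensity. The grade of an SAE is therefore seen mainly in the SAE listing (SAP 3.5.3), in the individual descriptions (Protocol 9.4.2) and, for treatment-emergent unsolicited events, in tables 15.3.1.4.5 and 15.3.1.4.6.

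Other outputs use a cut at Grade 3:
- the secondary endpoint of vaccine-related Grade 3 or 4 events within 28 days;
- the severe-event rows in SAP 3.5.9;
- listings 16.2.3.1.1.3 and 16.2.3.1.1.4.

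One limb of the halting rule in Protocol 4.5 also depends on Grade 3 or higher, for unexpected systemic reactions.

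**Working it through.** The plan gives no figure to reproduce. The check applies each rule in turn to the same unsolicited clinical event. The two right-hand columns apply the Appendix I rule on serious events under each meaning of *serious*.

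| Event | 8.2.5 alone | Appendix I estimating scale | Rule read as clinical gravity | Rule read as SAE definition |
|---|---|---|---|---|
| Life-threatening | 3 (highest available) | 4 | 4 | 4 |
| Hospitalised, not grave, stops daily activity | 3 | 3 | 3 | 4 |
| Hospitalised, not grave, Grade 1–2 by effect on activity | 1–2 | 1–2 | 1–2 | 4 |
| Diagnosis on the Appendix I list, Grade 1–2 by effect on activity | 1–2 | 1–2 | 4 | 4 |
| Not serious, not listed, Grade 1–2 | 1–2 | 1–2 | 1–2 | 1–2 |

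The rows show the following:

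1. **Missing Grade 4 alone (first row).** The event moves between 3 and 4. Any count of Grade 3 or higher is unchanged.
2. **SAE-definition reading (last column).** Every clinical SAE is Grade 4, so intensity is constant among them. Serious events of Grade 1–2 enter the Grade 3-or-higher counts.
3. **Gravity reading (fourth column).** Only the listed diagnoses cross the cut. For example, diffuse petechiae that do not interfere with daily activity are Grade 1 under 8.2.5 and Grade 4 here.
4. **Halting rule.** A vaccine-related SAE can lead to halting at any grade. The second limb needs an unexpected systemic reaction of Grade 3 or higher. A listed diagnosis that is not an SAE could meet that limb under one rule and miss it under the other.

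Size of one reclassified subject, with 30 per group (Protocol 9.2) and the Clopper-Pearson interval that SAP 3.5.9 uses for adverse-event incidence:

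- Change in the observed rate: 1/30 = 3.3 percentage points.
- Upper 95% limit at 0/30: 1 − 0.025^(1/30) = 11.6%.
- Upper 95% limit at 1/30: the 97.5th percentile of Beta(2, 29) = 17.2%.

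The documents give no frequency for SAEs of Grade 1–2 or for listed diagnoses of Grade 1–2, so no probability can be attached to this shift.

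**The case against.** The strongest defence is that the two scales are really one. Section 8.2.5 covers only events not represented in Appendix I and cites the whole appendix. Appendix I speaks of adverse events and clinical events as well as laboratory values. On that view a life-threatening clinical event is represented there and takes Grade 4, and only a cross-reference is missing. This reading is possible, but nothing states it. The appendix is titled for laboratory values, 8.2.8 ties it to measured toxicities, 9.4.2 points to Section 8.2 as a whole, and the SAP names no section.

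A second defence is that *serious* in Appendix I means grave. The rule relies on the clinician's judgement, its examples are mostly grave diagnoses, and it does not cite the SAE definition. This has force. A reader might infer that the protocol does make every clinical SAE Grade 4. The documents support that only as one of two readings. Nor does 8.1.2.1 exclude it outright: its main clause separates grade from seriousness, but the explanation that follows covers only the step from grade to seriousness.

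The consequences for analysis are limited. The primary analysis is descriptive (Protocol 9), and each SAE is listed and described individually, so a reader would see the grade beside the case.

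A reader might also infer that solicited events are exempt because they have their own scales. The rule covers any clinical event, so the exemption is not clear.

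**Conclusion.** The inconsistency stands and should be fixed. A life-threatening unsolicited clinical event has no single grade, and the Appendix I rule can set Grade 4 without regard to intensity. It does so for every clinical SAE under one reading and for the listed diagnoses under either.

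A reader might infer that the absent Grade 4 in 8.2.5 leads to undercounting of severe events. It does not, because an event at Grade 3 is already in every Grade 3-or-higher count. Only the Appendix I rule changes those counts, and only by moving Grade 1–2 events. The size is 3.3 points per subject in a group of 30, conditional on such an event occurring. No hypothesis test, power figure or sample size depends on it.

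The conflict in the text needs no assumption. The loss of information on SAE intensity assumes the SAE-definition reading. The effect on the halting rule assumes an unexpected, possibly related systemic reaction that one rule places below Grade 3 and the other at Grade 4.

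**What to change.** 1. Reconcile Protocol 8.1.2.1, 8.2.5 and the two Appendix I paragraphs into one intensity scale for clinical adverse events. Add Appendix I's existing Grade 4 text to 8.2.5, and reword the Appendix I rule so that meeting the SAE definition does not by itself set the grade.
2. Have the sponsor state how the diagnoses listed in Appendix I are graded, whether the rule applies to solicited events, and what follows for the grade-based limb of Protocol 4.5. The listed diagnoses should not be regraded without that statement, because lower grades could affect the halting criterion.
3. In SAP 3.5.9, name the governing protocol section instead of referring to the protocol as a whole.
4. Optionally, check the grades of recorded SAEs against the reconciled scale before database lock and keep the original grade in the listing.

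The cost is a short amendment or site memo, one line in the SAP and, if step 4 is taken, a query round whose size the documents do not give. The drawback of step 4 is a late review of grades in an open-label trial. Keeping the original grade makes any change visible. The laboratory tables need no change.
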